4.3 Measures to minimize bias

Different biases might arise in this project. To prevent selection bias and confounding in the two study arms, we will use stratified block randomization to balance the two arms with respect to important baseline characteristics. Due to the nature of the intervention, neither the participants, nor the data collectors of the study, nor the statistician can be blinded. However, to reduce selective counting of CFUs on the hand-rinse samples, the lab workers assessing the number of CFUs will be blinded.

In Module 1, the RANAS and well-being survey, we expect a recall bias and a desirability bias. To minimize the recall bias, participants will not be asked to report any events which have taken place longer than a week ago. To reduce the desirability bias, the people administering the survey will not label themselves clearly as Tdh or Cesvi staff members, because local people know that Tdh and Cesvi often delivers humanitarian aid in the region and might want to impress the Tdh and Cesvi teams. Additionally, to reduce any study personnel bias, the data collectors will all receive a training in advance. Their ID will be recorded in the survey form in order to be able to conduct quality control.

For Modules 1 to 3, data collectors have to upload the completed surveys every night, once they have a stable internet connection. All of the surveys will have the data collector's ID. The PhD student from Swiss TPH will control every second day how long the data collectors took to complete a survey, if certain answers are always the same for specific data collectors and the amount of missing data per survey. In addition, the GPS location of the tablet will be recorded to make sure that the data collection actually took place at the predefined location. These components will be correlated in the statistical software R (version 4.1.3) to test for significant differences between data collectors. In case a data collector delivers significantly different results which are not deemed realistic by the Swiss TPH study team and the local main correspondents of Tdh and Cesvi, the staff will be asked to comply with predefined rules once. If they still do not comply afterwards, they will be replaced. Faulty data from these staff members can then not be used any more for analysing the results of the H4H project. Modules 1-3 will be repeated three months after the intervention and nine months after the intervention.

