For Module 2, the handwashing observations, a Hawthorne effect is to be expected (the tendency of individuals to modify their behaviour due to their awareness they are being observed (McCambridge *et al.* 2014)). To minimise the Hawthorne effect, students will not be informed of being observed and the data collector will not get closer to the student being observed than needed to observe soap use. However, there is a possible source of bias resulting from the possibility of children connecting having someone close to the handwashing station with the intervention.

In Module 3, the microbiological analysis, a study personnel bias could influence the quality of the hand rinse samples and the accuracy of counting the CFUs. To be aware of differences between the data collectors, their ID will be stored during the sample collection on ODK. The number of CFUs per plate will be correlated with the people who collected the data to see if there are any significant differences between data collectors. The people counting the number of CFUs will be blinded and therefore do not know if the sample comes from the intervention or the control group. Additionally, every 10th sample will be duplicated during the data collection and the CFUs on every 10th plate will need to be counted additionally by another staff member as quality control.

To enhance the reliability of the outcomes from modules (1-3), it is proposed that each school be visited by two teams over two consecutive days for data collection. The first team of observers will conduct observations and collect hand rinse samples, while the second team of

interviewers will visit the same school on the following day to administer the RANAS and well-being survey to the students (as shown in Figure 3). This approach is recommended to avoid any potential positive impact on handwashing behaviour that may result from survey questions if students were surveyed first. Additionally, it will ensure that students' responses to the survey are not influenced as they will not be aware of being observed on the first day.

[figure not shown]

Figure 3: Flow-chart of data collection activities at baseline, follow-up and endline of the project depicting observations, the RANAS questionnaire and the hand-rinse samples.

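### Section 4.3 lets data judged faulty be excluded on criteria that could depend on outcome and arm, with no masked decision and no analysis with and without them

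*Combined protocol and SAP*

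**What the plan says.** Section 4.3 (Measures to minimize bias) describes checks on Modules 1 to 3 every second day. They cover time taken per survey, "if certain answers are always the same for specific data collectors and the amount of missing data per survey", and the tablet's GPS position. Then: "These components will be correlated in the statistical software R (version 4.1.3) to test for significant differences between data collectors". No model, school term, arm term, threshold or multiplicity rule is given.

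Removal follows a sequence:

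1. The trigger is "In case a data collector delivers significantly different results which are not deemed realistic by the Swiss TPH study team and the local main correspondents" (these correspondents belong to the two local partner organisations).
2. Next, "the staff will be asked to comply with predefined rules once".
3. After that single warning, "If they still do not comply afterwards, they will be replaced".
4. Finally, "Faulty data from these staff members can then not be used any more for analysing the results of the H4H project".

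The documents do not define faulty data or the predefined rules, and do not say whether all or only some of a collector's records go.

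The same section says that participants, collectors and the statistician cannot be blinded; only the laboratory staff counting colonies are. It says nothing about masking those who judge realism. Section 2.3 states that Swiss TPH leads the efficacy assessment and that the local partners support both the intervention and data collection.

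Sections 6.3.1 and 6.4 specify available cases under intention-to-treat principles without imputation, justified by expected loss to follow-up. Neither mentions exclusions for collector quality, and no sensitivity analysis for them is planned.

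**The concern.** Module 2 supplies the primary outcome, so the rule reaches the main comparison. The monitored components are mostly about process, but the trigger sentence speaks of results. If that word includes outcome values, people who may know the allocation can decide which outcome data look implausible. Collector differences can also contain school differences, which the plan itself assumes to be large (ICC 0.2), and arm differences, which the trial exists to find.

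Exclusion that depends on both outcome and arm biases the treatment comparison, and the random school effect in the primary model does not correct for it. If one observer or pair supplies all observations in a school, discarding their data can also remove that school's whole primary outcome.

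**Working it through.** **Inputs.** From Section 6.2: 20% v 45%, ICC 0.2, 50 students per school, 13 schools per arm, 80% power, 95% confidence level. From Sections 4 and 5.1: 25 students per school in Module 1 and 12 in Module 3. Not in the documents, so assumed: the number of collectors, schools per collector, and a beta-binomial distribution of school rates. The documents differ on whether 26 schools is the overall or the per-country total; 26 (13 per arm) is used here.

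**Plan's own figure.** Two-sided 5%, 80% power, 20% v 45% gives 54 students per arm without clustering. Design effect = 1 + (50 − 1) × 0.2 = 10.8. Schools per arm = 54 × 10.8 / 50 = 11.66, rounded up to 12, plus one for few clusters = 13. Simulated power (t-test on school proportions, 20,000 runs) is 82.0% with 13 and 78.3% with 12. The plan's figure is reproduced and is not in question.

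**Uniform answers as a check on a yes/no observation.** With ICC 0.2, the beta parameters sum to (1 − 0.2)/0.2 = 4, so a = 4p and b = 4(1 − p). The chance that all 50 students score no is B(a, b + 50)/B(a, b).

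| Arm | p | a, b | P(all 50 no) | Expected among 13 schools |
|---|---|---|---|---|
| Control | 0.20 | 0.8, 3.2 | 10.3% | 1.3 |
| Intervention | 0.45 | 1.8, 2.2 | 0.4% | 0.06 |

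Such a check would flag honest observers mainly in control schools. The figure is per school. For a collector judged over two independent control schools it falls to 0.103² = 1.1%, although the contrast between arms remains.

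**Flag rate if school is ignored.** If each collector covers whole schools and there is no true collector effect, a nominal 5% test that ignores clustering has size 2 × [1 − Φ(1.96/√DE)].

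| Students per school | ICC | DE | False flags |
|---|---|---|---|
| 50 | 0.20 | 10.8 | 55% |
| 50 | 0.10 | 5.9 | 42% |
| 50 | 0.01 | 1.49 | 11% |
| 25 | 0.20 | 5.8 | 42% |
| 12 | 0.20 | 3.2 | 27% |

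Over 26 schools at 20%, simulation gives at least one flagged collector in 56% of trials with 2 collectors, 93% with 4 and 99% with 6.

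**When collectors share schools.** Twenty-five interviews of at most 20 to 25 minutes take 500 to 625 minutes (8.3 to 10.4 hours) for one interviewer, and Section 4.3 describes a team visiting on one day. With five interviewers in each of 26 schools and five students each, the naive flag rate for a survey score is about 4%, 4% and 3% at ICC 0.05, 0.1 and 0.2. The inflation disappears.

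**What selective removal could do.** This is a deliberate worst case with no true effect and 20% in both arms. Dropping the lowest intervention school and the highest control school biases the difference by +4.9 points and raises the type I error from 5% to 12%. Dropping two in each arm gives +9.0 points and 28%. Loss of schools alone lowers simulated power from 82% (13 per arm) to 78% (12), 75% (11) and 70% (10).

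**The case against.** The strongest defence is that this is ordinary quality control with several gates. A significant difference removes nothing unless the results are also judged unrealistic, the collector has been warned, non-compliance continues and the collector is replaced. Staff are asked to follow rules, not to produce different results, and an honest collector in an unusual school can do that. Duration, missing data and GPS are process measures. No sentence says that handwashing prevalence is compared between collectors. All of this stands.

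A reader might infer more than the documents support:

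- *That the test ignores clustering.* It is unspecified, so this is an inference from silence.
- *That the judges know the allocation.* This is plausible from their roles but not stated. For the Palestinian baseline, Section 4 (Module 5) places the assessment before randomisation, so allocation cannot influence that round.
- *That colony counts can be discarded.* Section 4.3 does say "The number of CFUs per plate will be correlated with the people who collected the data", which compares an outcome between collectors, but attaches no exclusion rule.
- *That nearly every trial would have a flagged collector.* That holds with four or more collectors each covering whole schools, but not with two (56%) and not where interviewers share schools.

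The defence leaves two gaps. The later gates rest on undefined terms and an unmasked or unspecified judgement, so they do not rule out outcome-dependent exclusion. And for Module 2 the process evidence is thinner than it looks: Section 7.1 has observations written on paper and then entered on a tablet, so time and GPS may describe data entry. What remains is missing data and uniform answers, and uniform no-wash records may be genuine in control schools, which receive nothing for 12 months.

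**Conclusion.** The point holds as a weakness in the exclusion rule, not as a demonstrated bias. Section 4.3 permits exclusion of primary-outcome data after a comparison with no stated school or arm term and a realism judgement with no stated masking, and Section 6 provides no analysis that would reveal the effect.

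Its size is conditional. The 10.3% v 0.4% contrast rests on the plan's assumed rates and ICC, a beta-binomial model, and the uniform-answer check being applied to observations within one school. The 55% rests on collectors covering whole schools and on an outcome test that ignores clustering. It describes only the first gate; how often data would actually be excluded cannot be estimated from the documents. The bias and type I error figures are worst cases, not forecasts. This is a cheap improvement to the stated rule.

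**What to change.** Amend Sections 4.3 and 6.3.1:

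1. Compare collectors in a model that includes arm and a school effect.
2. Define faulty data by process evidence already collected, such as a GPS mismatch, implausible durations, or duplicated or fabricated records. Name the predefined rules and state which of a collector's records are removed.
3. Have the decision made by someone masked to arm and to outcome values.
4. Report exclusions by arm, and present the primary analysis with and without the excluded data.

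Which of the two analyses is labelled primary is a matter of choice, provided it is fixed in advance and both are shown. The cost is protocol wording, a masked decision-maker and one extra analysis. The downside is that some poor-quality data may be retained where no process criterion is met.

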In Module 4, students' hygiene-related health outcomes and absenteeism will be reported by one of the teachers in each school. To facilitate the process, a system of automatic weekly messages will be generated to remind teachers of filling out the absenteeism survey, and one of the tdh and Cesvi staff will follow and check their submissions on the ODK centre. However, different biases might arise. Depending on how dutifully the teachers report and on the severity of the health outcomes, a detection bias might occur. We will test for this bias by correlating the school with the proportion of reported days of absenteeism and health outcomes over a year. In order to intervene in case such differences exist, we will correlate the data in each quarter of the study year as a form of quality control. In addition, a form of selection bias can happen if a certain group of students falsely report a medical reason as an excuse for their absence on certain days. For example, a student might report his/her reason for being absent is being sick with any of the predefined hygiene-related health outcomes. To minimise such biases, the form of absenteeism that the teachers use contains a question about the availability of a medical report. If there is no medical report and the teacher still questions the reliability of the reason for the absence, they are asked to depend on their experience and knowledge to judge if the student's excuse is false or not. We are aware that this module is suboptimal due to the difficulty to confirm the reasons for the students' absenteeism. However, this is only part of an exploratory objective. We still think that if differences can be observed between the two intervention arms, this module is of high importance as it would demonstrate the significance of the H4H MCI in schools. If these differences can be demonstrated on a local level, motivating local schools and the Ministry of Education for future handwashing interventions might become easier.

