5.3 Exclusion criteria

Exclusion criteria Modules 1-4: included students must not fulfil any of the following exclusion criteria:

- Refusal to participate by not providing signed consent and assent forms
- Having any medical condition that prevents them from washing their hands
- Having unexplained intermittent attendance in school (school teachers will be consulted and the school's absenteeism records will be checked for that)

- Not being at the same school for the course of the study (1 year)

Exclusion criteria Module 5: Refusal to participate by the student or his/her parents.

Exclusion criteria Module 6: Refusals to participate.

Exclusion criteria Module 7: Refusals to participate

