6.1.2 Secondary hypotheses

Depending on the secondary objective, different secondary hypotheses were formed:

$H_{1,1}$ = There is a difference in well-being between the intervention and control groups of primary school students in Nigeria and Palestine.

$H_{0,1}$ = There is no difference in well-being between the intervention and control groups of primary school students in Nigeria and Palestine.

$H_{1,2}$ = There is a difference between hygiene-related RANAS variables between the intervention and control groups of primary school students in Nigeria and Palestine.

$H_{0,2}$ = There is no difference between hygiene-related RANAS variables between the intervention and control groups of primary school students in Nigeria and Palestine.

$H_{1,3}$ = There is association between personal, physical and social contextual factors and hand hygiene and the well-being of primary school students in Palestine.

$H_{0,3}$ = There is no association between personal, physical and social contextual factors and hand hygiene and the well-being of primary school students in Palestine.

$H_{1,e}$ = There is a difference in hygiene-related health outcomes and absenteeism between the intervention and control groups of primary school students in Nigeria and Palestine.

$H_{0,e}$ = There is no difference in hygiene-related health outcomes and absenteeism between the intervention and control groups of primary school students in Nigeria and Palestine.

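### The quarterly Module 4 check infers teacher under-reporting from school differences in the outcome itself, so true school variation or the intervention effect can trigger it

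*Combined protocol and SAP*

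**What the plan says.** Section 4.3 explains that Module 4 outcomes "will be reported by one of the teachers in each school" and names the resulting risk: "Depending on how dutifully the teachers report and on the severity of the health outcomes, a detection bias might occur". Two controls act on submission. Teachers receive automatic weekly reminders, and "one of the tdh and Cesvi staff will follow and check their submissions on the ODK centre".

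A third control is statistical: "We will test for this bias by correlating the school with the proportion of reported days of absenteeism and health outcomes over a year". It is repeated during the year: "In order to intervene in case such differences exist, we will correlate the data in each quarter of the study year". The section states no arm term, no size of difference that counts, no external standard for complete reporting, and no description of the intervention that would follow.

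Section 6.1.2 gives the alternative hypothesis for the same data: "There is a difference in hygiene-related health outcomes and absenteeism between the intervention and control groups of primary school students". Later in Section 4.3, a difference between arms is read as a sign of benefit: "We still think that if differences can be observed between the two intervention arms, this module is of high importance".

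School records are already used for another purpose. For the eligibility criterion on intermittent attendance, Section 5.3 says that the school's "absenteeism records will be checked for that".

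**The concern.** The bias named is a property of reporting, but the quantity tested is the outcome. With one teacher per school and schools as the randomised unit, a school's reported level mixes three things: how fully the teacher reports, how much illness there is, and which arm the school is in. A comparison of schools on that level cannot tell them apart. The same pattern could count as a sign of bias under the quarterly check and as a sign of benefit under the hypothesis.

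At stake is a feedback loop. If the intervention lowers illness, low-reporting schools will more often be intervention schools, and any follow-up aimed at low reporters would fall unevenly by arm. Section 4.3 also says that participants, data collectors and the statistician are not blinded, so nothing in the design hides the arm from those who run the check.

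**Working it through.** **Plan's own figure.** There is none to reproduce. The plan gives no expected absence rate, threshold or error rate for this check. The ICC of 0.2 in Section 6.2 is for observed handwashing and is not used here.

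**Comparison with the plan's other checks (Section 4.3).**
- Modules 1-3: a data collector's results must differ significantly and also be judged unrealistic before anything is done.
- Rule for schools with 25% higher negative health outcomes: the ministries are asked first whether this is usual.
- Module 4 quarterly check: neither step appears.

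**How often could it fire with perfect reporting?**

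Inputs from the documents:
- 26 schools of 50 students (Synopsis; Section 4 says 24 schools for Module 4 in one place and 26 schools per country in another).
- Rates expressed per 100 student-weeks (Section 4, Module 4).
- Handwashing effects cited in Section 2.1.1: diarrhoeal disease reduced by 30% to 48% (rate ratio, RR, 0.70 to 0.52); respiratory disease by 21% (RR 0.79).

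Assumptions not in the documents:
- Control rate of 1 or 2 episodes per 100 student-weeks.
- 9 school weeks per quarter.
- Poisson counts.
- Chi-square homogeneity test across schools at 5%.
- Between-school coefficient of variation (CV) of 0 or 0.25.

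Student-weeks per school and quarter: 50 × 9 = 450. Expected control count c: 450 × 1/100 = 4.5, or 450 × 2/100 = 9.

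With 13 schools per arm and no other variation, the school mean is m = c(1 + RR)/2, and each arm lies h = c(1 − RR)/2 from it. The test statistic is approximately non-central chi-square with 25 df and non-centrality 26h²/m. The 5% critical value is 37.65.

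| c | RR | m | h | 26h²/m | Fires per quarter |
|---|---|---|---|---|---|
| 4.5 | 0.79 | 4.03 | 0.47 | 1.44 | 8% |
| 9 | 0.79 | 8.06 | 0.95 | 2.88 | 11% |
| 4.5 | 0.70 | 3.83 | 0.68 | 3.10 | 12% |
| 9 | 0.70 | 7.65 | 1.35 | 6.19 | 21% |
| 4.5 | 0.52 | 3.42 | 1.08 | 8.87 | 31% |
| 9 | 0.52 | 6.84 | 2.16 | 17.73 | 65% |

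Simulation with Poisson counts, and gamma-distributed school rates where CV > 0, agrees with the table and adds:
- No effect, no school variation: 5% per quarter. Over four quarters, 1 − 0.95⁴ = 18.5% for at least one firing.
- School CV 0.25, no intervention effect: 24% (rate 1) to 51% (rate 2) per quarter.
- CV 0.25 and RR 0.70 to 0.52 together: 32% to 87% per quarter.
- Arm share of low reporters: for RR 0.70 to 0.52 and CV 0 to 0.25, intervention schools make up 69% to 92% of the five lowest-reporting schools, against 50% by chance.

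**Would adjusting for arm be enough?** Comparing schools only within arm returns the rate to about 5% when schools do not otherwise vary. In a run with 12 school weeks per quarter, 2 episodes per 100 student-weeks and CV 0.25, it still fires in 49% to 63% of quarters. Arm adjustment removes the reaction to the intervention but not the reaction to ordinary school differences.

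**The case against.** The strongest reply has four parts.

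**The text is milder than it may look.** A reader might infer that the team intervenes every quarter, or that any difference at all is declared bias. The documents do not say this. The check is quarterly, action is conditional on differences, and the section speaks of a test. This stands.

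**The harm is not documented.** A reader might also infer that low-reporting intervention schools will be pressed to report more and that part of the effect will be erased. Section 4.3 never describes the action. A neutral enquiry that confirmed complete reporting would change nothing. This stands: the firing rates show how often the check could be triggered, not how far the outcome would shift.

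**The arm effect may be small.** The 30-48% concerns diarrhoeal disease, whereas Module 4 also covers respiratory infections, helminths, head lice, trachoma and skin infections. Suppose the reduction e applies only to children who wash, and handwashing moves from 20% to 45% as in Section 6.2. The arm RR is then (1 − 0.45e)/(1 − 0.20e): 0.865/0.94 = 0.92 at e = 0.30, and 0.784/0.904 = 0.87 at e = 0.48. With no school variation the test fires in roughly 5-7% of quarters, hardly above its 5% floor. This stands as a limit on the intervention-effect route. It leaves the school-variation route untouched.

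**Other controls exist and the module is exploratory.** Weekly reminders and submission checks are described without restriction by arm, and Section 4.3 itself calls the module suboptimal. This stands, but following submissions does not show whether absences were left out of a submitted diary, and it does not make the outcome comparison a valid test of reporting.

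**Conclusion.** The point holds as a design weakness of minor consequence. As written, the quarterly check cannot identify the bias it names. It can be triggered by true school variation or by the effect that Section 6.1.2 hypothesises, and any resulting action could be unevenly distributed by arm.

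The firing rates are illustrative. They rest on assumed event rates, school weeks, school variation and a 5% test, and they run from close to the 5% floor for a small arm effect with homogeneous schools to well over half of quarters for large effects or heterogeneous schools. The conclusion that the check cannot separate reporting from outcome does not depend on those assumptions.

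The documents do not support a claim that the effect will be erased or that the trial's main result is threatened. The action is undescribed, the distortion cannot be sized, and the primary endpoint comes from the structured observations, which this check does not touch.

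**What to change.** Base the quarterly trigger in Section 4.3 on measures of reporting, not on outcome levels:

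1. The share of expected diary submissions received, counting explicit nil returns. Section 4.4 describes writing down absence events. A count of entries alone would fall when illness falls and bring the same problem back.
2. Agreement of total diary absences with the school's own attendance record, which is already consulted for eligibility.

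State what happens when a school falls short, apply the same query procedure in both arms, and report both measures by arm. If the comparison of outcome levels is kept, make it within arm only and use it as a prompt for a neutral query, not as evidence of bias.

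The cost is a change of protocol wording, a nil-return option in the diary, and a small quarterly comparison with school records. One limit remains: the attendance record may not verify the reason for an absence, so misattributed reasons would still go largely unchecked.

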Module 4: Diary approach for pre-defined hygiene-related health outcomes and absenteeism incidence: Longitudinal data on hygiene-related health outcomes and absenteeism will be collected over the study course (12 months) in both arms of the study. The main outcome of this objective is students' hygiene-related absenteeism. Absenteeism is hygiene-related if the student suffered from diarrhoea, respiratory tract infections, helminth infections, head lice, trachoma and skin infections. For the outcome of this objective an electronic/paper diary will be prepared by the PhD and used in each school by one of the teachers on a daily basis to report the absenteeism of included students in each cluster along with the reason for their absenteeism (pre-defined health outcomes). To adjust for the cluster design effect, we will calculate the rates of hygiene-related absenteeism separately for each medical reason for each school. This will be carried out by dividing the number of episodes of hygiene-related absenteeism for each medical reason by the number of student-weeks. The

answer will then be multiplied by 100 to obtain rates per 100 student-weeks and will be presented using descriptive statistics.

Module 5: personal, physical and social contextual factors survey: Handwashing behaviour and well-being of school children are not only influenced by the level of water access and psychosocial behavioural factors but also depend on culture- and context-related factors. The exceptional stressors forced by the prolonged military occupation in Palestine result in difficult personal, social and physical conditions which lead to disruption in different aspects of life beyond the school environment. The analysis of all possible determinants of hand hygiene behaviour and well-being at baseline before the start of the intervention will provide a better understanding of factors that potentially modify the effectiveness of an intervention and may need consideration for maximising effectiveness on hygiene and well-being when implementing larger-scale WASH interventions in the Palestinian context.

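### In Module 4, an unmasked teacher's ruling on doubted, undocumented absences feeds the only between-arm absence rates specified

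*Combined protocol and SAP*

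**What the plan says.** Section 4 (Module 4) defines the outcome: "The main outcome of this objective is students' hygiene-related absenteeism", meaning absence attributed to one of six listed conditions. A teacher uses the diary "on a daily basis to report the absenteeism of included students in each cluster along with the reason for their absenteeism"; a parenthesis then ties the reason to the pre-defined health outcomes. The rate comes from "dividing the number of episodes of hygiene-related absenteeism for each medical reason by the number of student-weeks", multiplied by 100. Section 6.3.1.1 repeats these rates, separately for each health outcome and by school, and adds a random effect linear regression for the intervention effect.

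Section 4.3 confirms that "students' hygiene-related health outcomes and absenteeism will be reported by one of the teachers in each school". Against false excuses, the form "contains a question about the availability of a medical report". If there is no report and the teacher still doubts the reason, "they are asked to depend on their experience and knowledge to judge if the student's excuse is false or not". On masking, the same section says that "neither the participants, nor the data collectors of the study, nor the statistician can be blinded".

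Section 4.3 also admits that reasons for absence are hard to confirm, calls the module suboptimal and the objective exploratory, and plans a quarterly correlation of school with reported absence. It then says that a difference between the arms would show the importance of the package and might help to motivate schools and the Ministry of Education.

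**The concern.** The ruling is offered as a way to reduce bias, but it places an open-label judgement inside the outcome. Section 4.3 does not name teachers among those who cannot be blinded. A school-wide programme of infrastructure and behaviour-change activities is nevertheless visible to them. A teacher who believes that the programme works may be readier to dismiss an illness excuse. A teacher made more alert to hygiene may be readier to accept one. Neither pull need be confined to one arm; it is enough that its strength differs between arms.

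At stake is how any difference in cause-specific absence is read. It could reflect how reasons were classified rather than how often pupils were ill, and the plan specifies no between-arm measure that would help to tell these apart.

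**Working it through.** **The plan's own figure.** The documents give no rate, effect size or power for absenteeism. Module 4 reuses the primary-endpoint sample (Section 6.2: 20% vs 45%, ICC 0.2, 50 students per school, 80% power, 95% confidence, two-sided assumed). The individually randomised size is 54 per arm. The design effect is 1 + (50 − 1) × 0.2 = 10.8, and 54 × 10.8 / 50 = 11.7, so 12 schools. One more for the t degrees of freedom gives the stated 13. The figure reproduces, but the point does not depend on it.

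**Where the ruling enters.** It needs two conditions: no medical report, and a teacher who doubts the reason. The plan does not say what happens to an absence ruled false. I assume that it is not counted as hygiene-related, since the ruling would otherwise have no purpose.

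**Effect on the rate ratio.** Let u be the share of illness absences without a report, and aC and aI the proportions of these accepted as genuine in control and intervention schools. If a share d of undocumented absences is doubted and a share f of those is ruled false, then a = 1 − d × f. For example, 20% doubted and half of them ruled false gives 1 − 0.20 × 0.50 = 0.90. With the same true rate in both arms,

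observed rate ratio = [(1 − u) + u × aI] / [(1 − u) + u × aC].

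For u = 0.5, aC = 0.9 and aI = 0.8 this is (0.5 + 0.40) / (0.5 + 0.45) = 0.90 / 0.95 = 0.947. The documents give none of these inputs, so the table shows assumed ranges:

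| Acceptance, control / intervention | u = 0.25 | u = 0.50 | u = 1.00 |
|---|---|---|---|
| 0.9 / 0.8 | 0.974 | 0.947 | 0.889 |
| 0.9 / 0.7 | 0.949 | 0.895 | 0.778 |
| 0.8 / 0.9 | 1.026 | 1.056 | 1.125 |

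All-cause absence, and a rate based on all stated reasons, do not contain aC or aI. Under the same null, this mechanism leaves their ratios at 1.00.

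**Chance of a false signal.** Further assumptions are 2 hygiene-related episodes per 100 student-weeks, 36 weeks (0.02 × 50 × 36 = 36 episodes per school), a between-school coefficient of variation of 0.3, 13 schools per arm and a school-level t-test. In simulation, the false-positive rate rises from about 5% to 7% at a ratio of 0.94, 13% at 0.89 and 42% at 0.78. At 0.89 it runs from 18% to 8% as the coefficient of variation goes from 0.2 to 0.5. These runs pool all medical reasons. The plan's separate rates would have fewer episodes each and so more noise.

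**Whether the planned checks would catch it.** The quarterly correlation compares schools. Each school sits in one arm, so a difference in classification between arms looks the same as a programme effect. Module 3, by contrast, has blinded colony counters and a second count of every tenth plate.

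**Whether another between-arm measure exists.** Total days absent appear only in that quality check. Absenteeism without a qualifier in Sections 4.2, 6.1.2 and 6.3.1.1 could be read more widely, but Section 4 defines the outcome as hygiene-related and no all-cause rate is given.

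**The case against.** The best defence is that the protocol has already conceded the weakness. Section 4.3 names teacher detection bias and false excuses, adds the medical-report question, has staff check submissions, and calls the module suboptimal and exploratory. Section 3.1.4 lists the objective as explorative, and Table 1 plans descriptive statistics only. This stands and lowers the priority. It does not settle the matter. The Synopsis makes this a secondary objective, Section 4.2 lists it among the main secondary endpoints, Section 6.1.2 gives it a hypothesis, and Section 6.3.1.1 fits a model.

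A reader might infer that the whole absenteeism outcome rests on teachers' opinions. The documents do not support that. Both conditions must hold before a ruling is made, and the share of absences that meets them is not stated. The 0.89 figure needs every illness absence to be undocumented.

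A reader might also infer that all-cause absence should become the lead measure. That would not answer the research question in Section 3.1.4, which concerns absence from hygiene-related infection, and it would dilute a true effect. Nor is it certain that the diary holds it. Daily logging of every absence is the natural reading of Section 4, but the parenthesis leaves this open and the form is not in the documents.

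Finally, recording reasons as stated shifts the classification to pupils and families who are themselves unblinded. That is a fair limit on the remedy.

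**Conclusion.** The point holds in a limited form. For doubted, undocumented absences, an unmasked teacher's ruling feeds the only between-arm rates specified, and the planned checks cannot separate its effect from that of the programme. The direction is unknown. Differences of 10 to 20 percentage points in acceptance between arms move a null rate ratio to between 0.97 and 0.78, or to between 1.03 and 1.13 if acceptance is higher in intervention schools. These figures rest wholly on assumed acceptance rates and undocumented shares. They show what is possible and do not predict that the result will be spurious or will favour the programme. The primary endpoint, observed handwashing before eating, is not touched. This is a minor-priority change, worth making because it is cheap.

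**What to change.** 1. **Sections 4.3 and 4 (Module 4) and the diary form.** Have the teacher enter the reason as stated, medical report yes or no, and any doubt as a separate flag that does not reclassify the absence.
2. **Section 6.3.1.1.** Report cause-specific rates by arm three ways: all stated reasons, excluding doubted ones, and documented ones only.
3. **Section 6.3.1.1.** Add an all-cause absence rate by arm as a companion to the cause-specific rates, after confirming that the form logs every absence. The school attendance records already consulted for eligibility (Section 5.3) could serve as a cross-check.
4. **Section 4.3.** Temper the statement about what a between-arm difference would show, unless these summaries agree.

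The cost is one diary instruction, one extra field and a few summaries. If the form does not log every absence, extending it adds some teacher time; Section 4.4 puts an entry at about one minute per student. All-cause absence remains open to differences in how diligently the diary is kept, and it dilutes a hygiene effect. Stated reasons remain open to reporting by unblinded pupils and families. The set of summaries therefore exposes the bias without removing it.
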